7.2.1.1. Estimand Framework

For the primary efficacy endpoint of the absolute change from baseline in pre-bronchodilator FEV1 at Week 24, intercurrent events may arise as a result of:

- i. Taking rescue medications with systemic corticosteroids and/or oral antifungal therapies (including an increase in dose) for asthma or ABPA for any reason
- ii. Taking prohibited medications
- iii. Discontinuing the study treatment

[figure not shown]
These intercurrent events will be handled using the treatment policy strategy as follows:

[figure not shown]
- i. All endpoint data collected after the use of rescue medication through Week 24 will be used in the analysis
- ii. All endpoint data through Week 24 will be included in the analysis irrespective of the use of prohibited medications
- iii. All endpoint data collected after treatment discontinuation through Week 24 will be used in the analysis

There are two ways in which missing data may arise: (i) patients who discontinue from the study prior to Week 24 will have (monotone) missing data from the last contact date through Week 24 and (ii) some intermittently missing data are expected due to patients occasionally missing a study visit or failure to obtain valid spirometry measurements at the study visit. For both types of missing data, the MMRM analysis model assumes that missing data are missing at random (MAR), that is, that patients with missing data at a given time point would have outcomes similar to those of patients in their treatment group with observed data at the given time point.

7.2.1.2. Sensitivity/Supplemental Analyses

[figure not shown]
A tipping point analysis will be performed as a sensitivity analysis of the primary efficacy endpoint of the absolute change from baseline in pre-bronchodilator FEV1 at Week 24 (provided that the results of the primary analysis described in Section 7.2.1 is statistically significant). The tipping point analysis will be implemented via a pattern-mixture model-multiple imputation approach as described in the steps below:

7.2.2. Secondary and Exploratory Efficacy Analyses

The secondary efficacy endpoint of the annualized rate of severe respiratory exacerbations over the 24-52-week treatment period will be analyzed using a negative binomial regression model. The response variable will be the total number of events occurring during the treatment period. The negative binomial regression model will include OCS use at screening, OAF use at screening, region, number of severe respiratory exacerbations requiring treatment with systemic corticosteroids in the 12 months prior to the screening visit, baseline eosinophil count, and treatment group as covariates. The natural logarithm of the number of days from the date of the first dose of study treatment (or date of randomization for patients who are randomized but not treated) to the date of the EOT visit (or date of last contact for patients who are lost to follow-up or discontinue from the study prior to the EOT visit) divided by 365.25 will be used as the value of the offset variable for each patient. The estimated annualized event rate within each treatment group and the corresponding 2-sided 95% CI will be derived from the model. For patients who permanently discontinue from study treatment, any off-study treatment severe respiratory exacerbation events that occur through the patient's EOT visit (or date of last contact for patients who are lost to follow-up or discontinue from the study prior to the EOT visit) will be included in the analysis. [REDACTED]

The secondary efficacy endpoints of the annualized rate of ABPA-related exacerbations (i.e., those that are associated with a doubling of serum total IgE from the prior pre-exacerbation value) over the 24-52-week treatment period and the annualized rate of severe respiratory exacerbations requiring either hospitalization or observation for >24 hours in an ED/urgent care facility over the 24-52-week treatment period will be analyzed in a similar manner as the

annualized rate of severe respiratory exacerbations. [REDACTED]
[REDACTED]
[REDACTED]
[REDACTED]
[REDACTED]. For each of the aforementioned

endpoints analyzed via negative binomial regression, if the model fails to converge, only descriptive statistics will be provided for the annualized rate of events in each treatment group.

[figure not shown]
To evaluate the absolute and/or percent change in the [REDACTED] efficacy/PRO/biomarker endpoints of the ACQ-5 score, the SGRQ total score, serum total IgE, serum *A. fumigatus*-specific IgE, FeNO, [REDACTED]
[REDACTED], within-group

point estimates of the mean change and corresponding 2-sided 95% CIs (based on the t-distribution) will be provided for each post-baseline time point at which the given parameter is collected (or as otherwise specified in Section 7.1). Patients must have both the baseline and at least 1 post-baseline measurement at the given post-baseline time point to be included in the summary of the mean absolute change/percent change from baseline at the given post-baseline time point. For analyses of percent change from baseline, if a patient's baseline value for a given parameter is 0, that participant will be excluded from the analysis of the given parameter at all post-baseline time points.

Per protocol, FeNO assessments should be conducted prior to spirometry and following a fast of at least 1 hour. For the purposes of the evaluation of the percent and absolute change from baseline in FeNO, FeNO assessments conducted after spirometry or after less than an hour fast will be excluded from the summary. Fasting status is recorded on the FeNO eCRF. For each applicable date, the timing of FeNO measurements will be compared to the timing of spirometry measurements to determine whether the FeNO assessment was conducted prior to spirometry.

To evaluate the secondary PRO endpoint of the proportion of participants who achieve a reduction in the SGRQ total score of ≥ 4 points from baseline at Weeks 12, 24, 36, and 52, within-group point estimates and 2-sided 95% CIs (based on the Wilson score confidence limits (Wilson, 1927)) will be provided for each of the specified time points. Patients with a baseline SGRQ total score less than 4 points will be excluded from the analysis. Patients must have both the baseline and at least 1 post-baseline measurement at the given post-baseline time point to be included in the calculation of the proportion at the given post-baseline time point.

[REDACTED]

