### **1. INTRODUCTION**

Allergic bronchopulmonary aspergillosis (ABPA) is a progressive, immunologic lung disease caused by hypersensitivity to the fungus Aspergillus fumigatus (A fumigatus) that occurs in patients with asthma or cystic fibrosis (Agarwal, 2014). The prevalence of ABPA is estimated to be 1% to 3% in patients with severe asthma referred for specialty care (Eaton, 2000) (Kurup, 2009). Clinically, asthma patients with ABPA have a more severe clinical course with poorly controlled asthma, poor response to treatment, and frequent episodes of exacerbations compared to patients with asthma who do not have ABPA. In addition, ABPA is often associated with thick mucoid secretions that can lead to obstruction of large and small airways, bronchiectasis (which does not otherwise occur in asthma), and lung function impairment beyond that seen in a typical asthma patient. A staging system is described for patients with asthma and ABPA to monitor disease progression clinically. Depending on the stage of the disease, clinical features in ABPA vary from mild asthma with occasional episodes of wheezing and cough, to patients with fibrosis, honeycomb lung, and respiratory failure (Patterson, 1982). Stage I is the initial acute stage of ABPA manifesting clinically with productive cough, wheeze, shortness of breath, fever, malaise, pleuritic chest pain, elevated serum immunoglobulin E (IgE), peripheral and tissue eosinophilia, and fleeting pulmonary infiltrates on imaging studies. In stage II, the disease goes into remission for a variable period; symptoms are reduced, the lung infiltrates clear, and the serum IgE value declines. Stage III is characterized by respiratory exacerbations with the recurrence of symptoms, production of thick sputum plugs, and an increase in serum total IgE levels that occur in up to 24% to 50% of patients each year (Agarwal, 2016) (Muthu, 2019). During episodes of exacerbations, thick brown mucoid sputum may contain A fumigatus hyphae. Stage IV is reached when, despite treatment, the disease progresses to extensive mucoid impaction of airways visible on chest x-ray or computed tomography (CT) imaging, lung function decline, and corticosteroid dependence. Stage V is the fibrotic stage. Unlike asthma, which does not progress to fibrotic lung disease, if the diagnosis is delayed or the disease is undertreated, ABPA progresses to a fibrotic end-stage lung disease that can lead to pulmonary hypertension, cor pulmonale, and respiratory failure.

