#### 3.3.1. Risk/Benefit for Dupilumab

Dupilumab has shown clinically relevant benefit in several type 2-mediated immune disorders including AD, bronchial asthma, CRSwNP, and eosinophilic esophagitis (EoE).

In adults and adolescents with moderate-to-severe uncontrolled asthma, dupilumab significantly reduced the risk of severe exacerbations compared to placebo and consistently improved lung function (FEV1), asthma control, and HRQoL in patients with a type 2 inflammatory signature as evidenced by a blood eosinophil count of  $\geq$ 150 cells/µL or a fractional exhaled nitric oxide concentration of  $\geq$ 25 parts per billion (ppb). In OCS-dependent patients with severe asthma, dupilumab significantly reduced the need for OCS by ~70% while at the same time reducing asthma exacerbations and improving FEV1 compared to placebo.

Type 2 inflammation plays a critical role in the pathogenesis of ABPA. The hypothesis that blocking key mediators of type 2 inflammation will lead to clinical benefit in patients with ABPA is supported by a post-hoc subgroup analysis from the completed dupilumab phase 3 pivotal study EFC13579 (QUEST) in patients with moderate-to-severe asthma who met the suggested criteria for ABPA diagnosis at baseline. The results from a total of 30 patients (n=18 in the combined dupilumab group and 12 in the combined placebo group) provide compelling clinical evidence for the efficacy of dupilumab in patients with ABPA. Dupilumab treatment compared to placebo showed an approximately 80% reduction in annualized severe exacerbation events and a 0.26L improvement in change from baseline to week 24 in pre-bronchodilator (BD) FEV1. In clinical practice, serum total IgE, which is elevated in patients with ABPA, is monitored to assess ABPA disease activity. Dupilumab suppressed serum total IgE by approximately 70% from baseline over a 52-week treatment period. Overall, dupilumab was well tolerated in this subgroup of patients with ABPA.

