# 6. STUDY DESIGN

### 6.1. Study Description and Duration

This phase 2, global, multicenter, randomized, double-blind, placebo-controlled study of dupilumab is designed to evaluate the efficacy and safety of dupilumab in patients with ABPA. Approximately 60 patients will be enrolled in the study. The study consists of 3 study periods:

- Screening period (4 weeks)
- Randomized treatment period (24- to 52 weeks)
- Post-treatment follow-up period (12 weeks)

This study employs a variable treatment duration from 24- to 52 weeks. Patients enrolled in the trial will remain in the treatment period for up to a maximum of 52 weeks or until the last patient completes a minimum treatment period of 24 weeks. Of note, the accrual and drop-out rates will be closely monitored. The maximum treatment duration of 52 weeks will not be changed. For further explanation regarding the duration of the randomized treatment period, refer to Section 9.1.1.

Patients who meet the eligibility criteria will be randomized (1:1) to 1 of the following treatment groups:

- Dupilumab 300 mg, after a loading dose of 600 mg on day 1, administered SC Q2W
- Matching placebo, administered SC Q2W

Randomization will be stratified by region (pooled country), chronic systemic corticosteroid use (yes/no) at screening, and by oral antifungal use (yes/no) at screening.

Rescue courses of systemic steroids for exacerbations, as determined by the investigators, will be permitted during the study. Patients will be required to continue all background asthma controller medications (ICS) with or without long-acting beta agonist (LABA), leukotriene receptor antagonist (LTRA), or long-acting muscarinic receptor antagonist (LAMA) without any changes in the dose or regimen during the study period. However, if 2 or more exacerbations occur during the treatment period, changes to background therapy (eg, changes to background asthma controller medication or initiation of antifungal therapy) may be made at the investigator's discretion.

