# 7. SELECTION, WITHDRAWAL, AND REPLACEMENT OF PATIENTS

#### 7.1. Number of Patients Planned

Approximately 60 patients (approximately 30 patients per arm) will be enrolled globally.

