11.5. Pooling of Categorical Variables for Statistical Analyses

For any analysis models that adjust for the region stratification factor, the regions of Asia and Eastern Europe will be pooled into a single “Non-Western Countries” level.

**12. TECHNICAL DETAILS PERTAINING TO INTERIM
ANALYSIS/(ES)**

No interim analysis is planned for this study.

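### The ABPA-related and hospitalised/ED exacerbation rates may be left with no interval, or a degenerate one, if events are few, because the only visible fallback is triggered by non-convergence alone

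*SAP*

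**What the plan says.** SAP Section 7.2.2 sets out the model for all severe exacerbations: "The negative binomial regression model will include OCS use at screening, OAF use at screening, region, number of severe respiratory exacerbations" in the year before screening, "baseline eosinophil count, and treatment group as covariates". The offset is log time in the treatment period, and the planned result is each group's annualized rate with a model-based two-sided 95% CI.

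The ABPA-related rate and the hospitalised/ED rate are handled the same way, and SAP Appendix 14.1 repeats the identical covariate list for both. For region, SAP Section 11.5 states that "the regions of Asia and Eastern Europe will be pooled into a single" level, so region takes one parameter. The model therefore has seven mean parameters (intercept plus six terms) and a dispersion parameter, eight in all.

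The visible fallback, for every endpoint fitted this way, is that "if the model fails to converge, only descriptive statistics will be provided for the annualized rate of events in each treatment group". The standard descriptive statistics in SAP Section 4 do not include a confidence interval.

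**The concern.** Convergence is the wrong signal for sparse counts. When one arm has no events, its log-likelihood contribution (for dispersion α) is −Σ (1/α) ln(1 + α·μᵢ). This keeps rising as the treatment coefficient goes to minus infinity, so there is no finite maximum-likelihood estimate. The same holds for the coefficient of any OCS, OAF or region level without events. An optimiser can stop on this flat ridge and report success, with a rate near zero and an interval that means nothing. If it reports failure instead, the plan drops the interval.

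Two secondary objectives, ABPA-related exacerbations and hospital/ED/urgent-care use, are reported through these rates and intervals. A stronger drug effect makes an empty dupilumab arm more likely. Elsewhere the SAP is better protected: the primary MMRM has an ordered list of alternative covariance structures, and the SGRQ responder proportion uses Wilson limits, which remain usable at zero.

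**Working it through.** **The plan's own figure.** The documents give no expected count, rate or precision for either endpoint. The stated 96% power concerns FEV1 only. Its SD, difference and dropout rate are blacked out, and it has no bearing here.

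**Inputs from the documents**
- Size: "Approximately 60 patients (approximately 30 patients per arm) will be enrolled globally" (Protocol Section 7.1).
- Follow-up: "This study employs a variable treatment duration from 24- to 52 weeks" (Protocol Section 6.1).
- Proxy for the placebo rate: stage III exacerbations with "an increase in serum total IgE levels that occur in up to 24% to 50% of patients each year" (Protocol Section 1). Read directly as events this is 0.24-0.50 per year; converted by −ln(1−p) it is 0.27-0.69.
- Proxy for the effect: "Dupilumab treatment compared to placebo showed an approximately 80% reduction in annualized severe exacerbation events" (Protocol Section 3.3.1), a rate ratio of 0.2.

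**Assumptions.** Follow-up uniform over 24-52 weeks; dispersion 1; a rate ratio of 0.5 as the weaker alternative.

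**Person-time per arm of 30.** All at 24 weeks: 30 × 168/365.25 = 13.8 years. All at 52 weeks: 30 × 364/365.25 = 29.9. Uniform: (13.8 + 29.9)/2 ≈ 21.8.

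**Chance of an empty dupilumab arm.** With dupilumab rate r and follow-up uniform from a = 0.460 to b = 0.997 years, P₀ = { ln[(1+rb)/(1+ra)] / [r(b−a)] }³⁰. For r = 0.24 × 0.2 = 0.048 the bracket is 0.9663, and 0.9663³⁰ ≈ 0.357.

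| Placebo rate/yr | Rate ratio | Expected dupilumab events | P(zero events) |
|---|---|---|---|
| 0.24 | 0.2 | 1.05 | 35.7% |
| 0.27 | 0.2 | 1.18 | 31.5% |
| 0.50 | 0.2 | 2.18 | 12.2% |
| 0.69 | 0.2 | 3.02 | 5.7% |
| 0.24 | 0.5 | 2.62 | 8.2% |
| 0.50 | 0.5 | 5.46 | 0.7% |

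At the extremes of follow-up, using the Poisson form exp(−E) at rate ratio 0.2: 0.27/yr with everyone at 24 weeks gives E = 0.76 and 47%; 0.69/yr with everyone at 52 weeks gives E = 4.14 and 1.6%.

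**Does non-convergence catch it?** In 306 simulated datasets with no dupilumab events, a full negative binomial fit by BFGS reported convergence in 117. A fixed-dispersion iteratively reweighted fit reported it in all 306, with treatment coefficients near −22 and standard errors above 10,000. A separate run gave 143 of 144, with a standard error near 15,000.

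**Empty covariate levels add to this, by an amount the visible text does not determine.** Simulating the six-term model (assumed: OCS 30%, OAF 30%, region 40%, dispersion 0.5-1.0), I counted trials with no finite estimate or with an upper/lower CI ratio above 100.
- Rate ratio 0.2: about 59% at 0.27/yr, 24-30% at 0.45/yr, 8-11% at 0.69/yr.
- Rate ratio 0.5: 25-27%, 6-8% and 2%.

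How the arm rate is averaged over covariates matters. At 0.24/yr and rate ratio 0.5, with dispersion fixed at 1 and the same prevalences, balanced least-squares means were unusable in 32% of trials. Averaging over the observed covariates gave 8%, essentially the empty-arm share.

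**What an exact interval would give.** With zero events the upper 95% Poisson limit is −ln(0.025)/person-years = 3.69/person-years: 0.27 per year at 13.8, 0.17 at 21.8 and 0.12 at 29.9. All are finite and informative.

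**The case against.** Several points on the other side stand.

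- **Blacked-out text.** Lines are blacked out directly before the fallback sentence. A reader might infer that the plan has no other provision for sparse counts. The documents do not support that; only the visible rule can be judged. That rule does follow the blacked-out lines and covers all the negative binomial endpoints.
- **Frequency.** A reader might infer that the planned analysis will often fail. No rate is stated for either endpoint. The 24-50% is a background percentage of patients, and the 80% comes from a post-hoc subgroup of 30 patients and concerns all severe exacerbations. Entry requires a severe exacerbation in the past year or chronic OCS, and OCS is tapered from week 4; either could raise the rate. Against that, SAP Section 7.1.2 counts an event with no IgE sample within 30 days as not ABPA-related, which lowers the count. Hospitalised events may be rarer still, but any rate for them is an assumption.
- **Stakes.** Amendment 3 removed the placebo comparison for secondary endpoints as underpowered, and there is no multiplicity-controlled test. Nor does the fallback leave nothing: descriptive annualized rates are still reported, and an interval could be added at reporting. It would then be chosen after the counts were known.
- **Overcorrection.** Stepping down whenever either arm has fewer than five events would fire in about 81-99% of trials at an 80% reduction, nearly replacing the planned model. Exact Poisson limits in both arms would also under-cover placebo: 91-93% at 0.50-0.69/yr with dispersion 1.

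These points limit the size of the concern and shape the remedy. They do not remove the gap: followed literally, the visible rule gives a meaningless interval or none when an arm is empty.

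**Conclusion.** The concern holds in a limited form: if events are few, the visible plan may give no interval, or a degenerate one, for the ABPA-related and hospitalised/ED rates. For ABPA-related events, a zero-event dupilumab arm would occur in roughly 6-36% of trials with an 80% reduction and placebo rates of 0.24-0.69 per year. With a 50% reduction and 0.24-0.50 per year the share is about 1-8%. These figures rest on proxy rates, about 22 patient-years per arm and dispersion 1. Empty covariate levels can raise the share of unusable intervals, by an amount that depends on unstated prevalences and on how adjusted rates are averaged. No figure can be derived from the documents for hospitalised/ED events.

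A reader might also take this as a threat to error control. It is not: these are within-group estimates with no between-group test. The harm is lost or misleading precision for two secondary objectives.

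**What to change.** Keep the planned negative binomial model as the primary analysis of both endpoints. In SAP Section 7.2.2, extend the fallback trigger to any of:

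- non-convergence (as now);
- zero events in an arm, or in a level of OCS, OAF or region;
- a non-finite standard error, or a standard error of the log rate above a stated limit, for example 5. That limit is loose: exp(1.96 × 5) puts each confidence limit a factor of about 18,000 from the estimate, so it catches only degenerate fits.

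When triggered, report each arm's events, person-years and crude annualized rate with a 95% CI. Use an exact (Garwood) Poisson interval for an arm with zero or very few events, with that number stated in advance. Use an overdispersion-robust interval, such as an intercept-only negative binomial or a robust-variance rate, for an arm with more. If the blacked-out lines already contain such a rule, a cross-reference is enough.

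The cost is SAP wording and a few lines of code. The downside is that, when the step-down applies, the interval is unadjusted and is conservative in the sparse arm.

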8. HYPOTHESIS TESTING METHODS AND MULTIPLICITY CONTROL

See Section 1.2 and Section 7.2.1 for information related to the hypothesis testing methods used in this study. Control of multiplicity is not applicable.

9. SUMMARY OF EXPOSURE DATA

9.1. Study Drug Exposure and Compliance

Study drug exposure and compliance will be summarized by treatment group for the SAF population.

The duration of exposure to study treatment (in days) during the study will be presented by treatment group and calculated for each individual patient as:

(Date of last study drug administration – date of first study drug administration) + 14 days

The calculation does not take into account temporary dosing interruptions (including dosing interruptions due to COVID-19).

The number and percentage of patients randomized and exposed to double-blind study drug will be presented by the following, cumulative, duration of exposure categories: ≥ 14 days, ≥ 28 days, ≥ 42 days, etc., with a 14-day increment added for each subsequent category. The highest category displayed will account for the maximum duration of exposure observed in the study.

In addition, duration of exposure to study treatment during the study will be summarized for each treatment group by the following summary statistics: arithmetic mean, sample SD, minimum, Q1, median, Q3, and maximum.

Compliance with the study drug will be calculated as follows:

(Number of study drug injections during the exposure period)/(Number of planned study drug injections during the exposure period) $\times 100\%$

The number of study drug doses administered and treatment compliance will be summarized for each treatment group by the following summary statistics: arithmetic mean, sample SD, minimum, Q1, median, Q3, and maximum. Treatment compliance will also be presented by the following ranges: $<80\%$ and $\geq 80\%$.

